## 9.8. Concomitant Medications

Information regarding medications taken by the subject throughout the study will be collected and recorded on the Prior/Concomitant Medications CRF. This information will include the name of the medication, dosage information (including frequency and route of administration), dates taken, reason for use, and stop date, if available.

As a general rule, any new medication initiated during the course of the study should be to treat an AE. Hence, the start date of a new concomitant medication should always coincide with a date of an AE, including an MS exacerbation or worsening of MS. Changes to existing, or initiation of new, MS medications (including disease modifying and symptomatic) should only be made after Week 12. If new MS medications are initiated during study participation, please inform the Medical Monitor in a timely manner.

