## 9.7. Prohibited Medications and Restrictions

The following medications are prohibited during study participation:

- Amantadine, other than provided study drug
- Live attenuated influenza vaccine

Medications that may affect urinary pH, including, but not limited to, carbonic anhydrase inhibitors, sodium bicarbonate, urinary acidification agents, quinine, quinidine, triamterene, or trimethoprim, can affect the elimination of ADS-5102. The excretion rate of amantadine increases rapidly when the urine is acidic, hence, the administration of urine acidifying drugs may increase the elimination of the drug from the body. Alterations of urine pH towards the alkaline condition may lead to an accumulation of the drug, with a possible increase in adverse reactions. Consequently, subjects should be monitored for changes in efficacy or adverse reactions under conditions that alter the urine pH to more acidic or alkaline, respectively.

Products with anticholinergic properties may potentiate the anticholinergic-like side effects of amantadine. Subjects should be monitored for anticholinergic effects. The investigator should consider reducing the dose of anticholinergic drugs, if atropine-like effects appear when these drugs are used concurrently.

While taking study drug, **concomitant use with alcohol is not recommended**, as it may increase the potential for CNS effects such as dizziness, confusion, lightheadedness, and orthostatic hypotension and may result in dose-dumping.

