#### **13.1.1. Adverse Event (AE) Definition**

Any medical condition or clinically significant laboratory abnormality with an onset date before the first date of study drug administration is usually considered to be pre-existing, and should not be documented in the CRF as an AE.

An AE **does** include:

- an exacerbation of a pre-existing illness;
- an increase in frequency or intensity of a pre-existing episodic event or condition;
- a condition detected or diagnosed after study drug administration even though it may have been present prior to the start of the study;
- persistent disease or symptoms present at baseline which worsen following the start of the study.

An AE **does not** include:

- medical or surgical procedures (eg, surgery, endoscopy, tooth extraction, transfusion)  
Note: in this case, the condition that led to the procedure is an AE;
- pre-existing diseases or conditions present or detected prior to start of study drug administration, which do not worsen;
- the disease or disorder being studied or a sign or symptom associated with that disease (ie, signs or symptoms associated with lack of efficacy will generally be considered to reflect underlying disease, rather than AEs, and are considered anticipated);
  - In this study, walking ability is an efficacy parameter and changes in this measure (both positive and negative) will be reported as efficacy outcomes. Worsening of other MS-associated parameters should be reported as AEs
- situations where an untoward medical occurrence has not occurred (eg, hospitalization for elective surgery, elective abortion, social, and/or convenience admissions);
- overdose of either study drug or concomitant medication without any signs or symptoms. (Dosing details will be recorded on the appropriate eCRF(s)).
- pregnancy - Pregnancy in itself is not regarded as an AE unless there is a suspicion that an investigational product may have interfered with the effectiveness of a contraceptive medication (see [Section 13.3.3](#)).

All AEs must be fully and completely documented on the AE page of the CRF and in the subject's medical notes. The following attributes must be assigned: description of AE, dates and times of onset and resolution (or whether ongoing), severity ([Section 13.1.6](#)), relationship to study drug ([Section 13.1.7](#)), whether an SAE or not (Section 13.1.2, and action taken (ie, no action taken; study drug interrupted; study drug discontinued; other).

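### The rule in Section 9.8 that a new medication's start should always match an AE date conflicts with the AE definition in Section 13.1.1 and should be reconciled with it

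*Combined protocol and SAP*

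**What the plan says.** Section 9.8 states a general expectation: "As a general rule, any new medication initiated during the course of the study should be to treat an AE". The next sentence turns it into a rule about dates: "Hence, the start date of a new concomitant medication should always coincide with a date of an AE". That sentence closes by spelling out what such AEs cover: "including an MS exacerbation or worsening of MS". The sentence after that deals with MS treatment: "Changes to existing, or initiation of new, MS medications (including disease modifying and symptomatic) should only be made after Week 12". The same section has sites record a reason for use for each medication and asks that the Medical Monitor be told of new MS medications.

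Section 13.1.1 defines what is and is not an AE. On walking ability it says that "changes in this measure (both positive and negative) will be reported as efficacy outcomes", while worsening of other MS parameters is to be reported as AEs. It also excludes "pre-existing diseases or conditions present or detected prior to start of study drug administration, which do not worsen", and situations in which nothing untoward has happened.

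Section 9.7 prohibits two items only: amantadine other than study drug, and "Live attenuated influenza vaccine".

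Under Section 13.2.1 an AE that occurs after the first dose in this study is a treatment-emergent AE (TEAE). Section 14.6 summarises TEAE incidence by treatment sequence and overall.

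**The concern.** A general rule admits exceptions; a rule that holds always does not. Section 9.8 moves from the first to the second with the word Hence, and the second half is the part that a site or monitor can check against the case report form (CRF). It also treats worsening of MS as an AE without setting walking apart, although Section 13.1.1 does exactly that. Every subject in this trial has MS with walking impairment, so the two sections collide on the condition under study.

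What is at stake is consistent AE recording. The primary objective is safety and tolerability, and TEAE incidence is its main summary. If some of the roughly 80 sites enter an AE because a drug was started, and others enter one only when Section 13.1.1 is met, the counts partly reflect prescribing and site habit.

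**Working it through.** No figure in the plan bears on this point, so there is none to reproduce. The check sets Section 9.8 against Section 13.1.1 for each kind of new medication.

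| Reason for the new medication | Section 9.8 | Section 13.1.1 | Conflict? |
|---|---|---|---|
| Symptomatic MS drug after Week 12, for walking alone | Contemplated; AE date expected | Walking change is an efficacy outcome | Yes, the clearest case |
| MS drug for an exacerbation, or worsening other than walking | Contemplated after Week 12; AE date expected | Is an AE | No |
| Substituted drug for a pre-existing condition that has not worsened | AE date expected, if a substitution counts as new (not stated) | Not an AE | Yes, on that reading |
| Influenza vaccine other than the live attenuated type | AE date expected; not on the Section 9.7 list | No untoward occurrence | Yes, by implication |

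For the first row, Section 5.1 names an approved drug for walking impairment in MS, and Section 9.7 does not list it. Section 8.5 narrows the case, because a need for a drug that could disturb the study measurements is one possible reason to stop study drug. It does not remove the case: Section 8.5 depends on the judgement of the investigator or sponsor, and Section 9.8 asks only that the Medical Monitor be informed.

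A site facing the first, third or fourth row has three courses:

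1. Enter an AE to satisfy Section 9.8. If dated after the first dose, it is a TEAE under Section 13.2.1 and is counted under Section 14.6.
2. Treat the start as a departure from Section 9.8. If judged significant, it is listed under Section 14.10. It affects the per-protocol set (Section 14.2) only if judged major and able to confound the Week 52 efficacy assessment.
3. Record the medication and its reason for use, and nothing more.

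The text does not choose among these.

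For scale only, let p be the proportion of subjects with at least one such start, q the share of those for whom the site enters an AE, and g the share of subjects with such an entry who already have a genuine TEAE. The rise in the proportion with any TEAE is

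rise = p × q × (1 − g).

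The documents give none of the three. The ceiling is q = 1 and g = 0, where the rise equals p. The protocol's upper figure is about 540 eligible subjects. With p assumed at 5%, 10% or 20%:

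- 540 × 0.05 = 27 subjects, at most 5 percentage points
- 540 × 0.10 = 54 subjects, at most 10 points
- 540 × 0.20 = 108 subjects, at most 20 points

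These are ceilings under assumed rates, not estimates.

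**The case against.** The strongest reply is that Section 9.8 never tells anyone to create or re-date an AE. It says should, it follows from a rule stated as general, and it refers to a date of an AE, which need not be the onset, so treating an ongoing AE satisfies it. It can be read as limiting new medication, in which case a start without an AE is a deviation. What counts as an AE is governed by Section 13.1.1; onset is reported separately for each AE under Section 13.2.1; and reason for use already identifies starts made for other reasons. Permission for such starts is mostly implied, by the short prohibited list and the Week 12 sentence. All of this stands, and it limits the point.

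A reader might go further and infer that Section 9.8 obliges sites to attach an AE to every new medication and so produces spurious TEAEs. The documents do not support that: it drops the hedge, and it assumes that sites override Section 13.1.1. A reader might also infer that such entries would dilute differences between treatment sequences. Nothing supports that either. No prescribing rate by sequence is given, and Section 14.6 plans incidence summaries, not a between-sequence test.

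What the reply does not remove is the case of a drug started for walking alone. There the two sections give different answers, and reading Section 9.8 as a restriction only moves the inconsistency from AE recording to deviation recording.

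**Conclusion.** The point holds as a conflict between two stated rules. The unqualified date rule in Section 9.8 cannot be squared with Section 13.1.1 for a symptomatic MS medication started after Week 12 for walking alone. The same tension arises, less directly, for other starts with no qualifying event. The consequence is a risk that AEs excluded by Section 13.1.1 are recorded at some sites and counted as TEAEs, while other sites handle the same start differently.

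The size is unknown. It depends on how often such medications are started, how literally sites apply Section 9.8, and how many of the affected subjects already have a genuine TEAE. The direction of any effect by sequence cannot be determined either. This is a minor point, worth acting on because the affected count is the main summary for the primary objective and the remedy is small.

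**What to change.** Reconcile Section 9.8 with Section 13.1.1 by replacing the date sentence with wording such as:

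> Record the reason for use of each new medication; link it to an AE only if the treated condition meets the AE definition in 13.1.1, and report the AE onset as the date the event began, not the date the medication started.

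This changes documentation only. It leaves untouched which medications are allowed and when MS treatment may change.

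The cost is one sentence of protocol text, plus a revised data check if one has been built on the present rule (the documents describe none). Reason for use and AE onset are already collected, so no new field is needed. The downside is that monitors could no longer assume that every new medication has a matching AE; they would have to read the recorded reason when looking for unreported events.

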## **9.9. Treatment Compliance**

Subjects will be instructed to return all used/unused blister cards or bottles at the next study visit, when the designated study site staff will review the number of returned capsules to assess subject compliance.

## **9.10. Randomization and Blinding**

This is an open-label study, during which all subjects will receive ADS-5102 titrated to a dose of 274 mg/d.

## 10. ASSESSMENT OF EFFICACY

Evaluations relating to efficacy to be performed during the study are described in the following table, and should be performed in the order shown: MSWS-12, T25FW, TUG, and the 2MWT. Full details on how efficacy assessments are to be performed will be provided in the study manual.

**Table 3: Efficacy Assessments**

Assessment	Study Visit	Description
Timed 25-Foot Walk (T25FW)	Baseline/Week 0 Week 12 Week 24 Week 52 (or ET) Safety Follow-Up	The T25FW is a measure of lower extremity function. The subject is directed to a clearly marked 25-foot course and is instructed to walk 25 feet as quickly as possible, but safely. The task is immediately administered again by having the subject walk back the same distance. The result is reported as time to complete (seconds) or speed (feet per second). Improvement is indicated by a decrease in time or an increase in speed.
Timed Up and Go (TUG)	Baseline/Week 0 Week 12 Week 24 Week 52 (or ET) Safety Follow-Up	The TUG is a measure of lower extremity strength, balance, and coordination. The subject stands up from a chair, walks 3 meters then turns around and walks back to the chair to sit down. The result is reported in seconds. Improvement is indicated by negative change scores.
2-Minute Walk Test (2MWT)	Baseline/Week 0 Week 12 Week 24 Week 52 (or ET) Safety Follow-Up	The 2MWT is a measure of lower extremity function. The subject is instructed to walk as far as possible in 2 minutes, and the distance is measured in meters. Improvement is indicated by positive change scores.
Multiple Sclerosis Walking Scale-12 (MSWS-12)	Baseline/Week 0 Week 12 Week 24 Week 52 (or ET) Safety Follow-Up	The MSWS-12 is a 12-item walking scale that is a measure of patient-reported walking ability during the past 2 weeks. Each item is scored on a 1 to 5 scale. A total score can be generated and transformed to a 0 to 100 scale. Improvement is indicated by negative change scores.

## 11. ASSESSMENT OF SAFETY

### 11.1. Physical Assessments Relating to Safety

Procedures that are shared between Week 16 of Study ADS-AMT-MS301 and the Baseline visit of the present study do not need to be repeated and the data will be captured in both studies.

#### 11.1.1. Scheduled Physical Assessments Relating to Safety

Physical examinations relating to safety to be performed during the study are described in the following table.

**Table 4: Physical Examination Assessments Relating to Safety**

Assessment	Study Visit	Description
Complete physical examination	Baseline/Week 0 Week 52 (or ET)	Physical examination including: skin, head-neck, eyes-ears-nose-throat, lungs-chest, heart, abdomen, extremities.
Symptom-directed physical examination, as needed	Weeks 4, 12, 24, and Safety Follow-Up	Physical examination adequate to evaluate fully the diagnosis and severity of an AE or AEs having occurred up to the date of the visit.
Weight	Baseline/Week 0 Week 52 (or ET)	Weight will be recorded in kilograms. Subjects may be weighed in their undergarments or in light clothing (no jackets or shoes). Measuring weight must be done consistently, using the same set of weighing scales when possible.
Vital signs	Baseline/Week 0 Week 4 Week 12 Week 24 Week 52 (or ET) Safety Follow-Up	Systolic and diastolic blood pressures, heart rate, and body temperature should be recorded after the subject has been seated quietly for at least 5 minutes. Blood pressure, respiratory rate, heart rate, and temperature will be measured once each day assessed.

**Table 4: Physical Examination Assessments Relating to Safety (Continued)**

Assessment	Study Visit	Description
Expanded Disability Status Scale (EDSS)	Week 52	The Expanded Disability Status Scale (EDSS) is an ordinal scale, 0 to 10, based on a comprehensive neurological examination, used to quantify disability in multiple sclerosis. The EDSS utilizes scoring in 8 functional systems (visual, brainstem, pyramidal, cerebellar, sensory, bowel and bladder, cerebral, and other) and ambulation. A score of 0 indicates a normal neurological exam and a score of 10 is death. EDSS steps 1 to 4.5 are defined by functional system scoring in patients who are fully ambulatory. EDSS steps 5.0 to 9.5 are defined by the extent of walking impairment.

### 11.1.2. Unscheduled Physical Assessments Relating to Safety

If, at a scheduled or unscheduled study visit, a subject reports experiencing, or having experienced, an AE, or is observed to be having an AE, the investigator should perform those examinations necessary to evaluate fully the diagnosis and severity of the AE.

If the AE is one of dizziness, lightheadedness, pre-syncope, syncope, or a related event, the examination must include, at a minimum, testing for orthostatic hypotension. After the seated blood pressure has been obtained, the measurement will be repeated within 3 minutes of the subject standing up. This procedure may be repeated, if appropriate, following hydration. If repeated, a total of two additional pairs of blood pressure assessments (sitting/standing) should be obtained, and the results of the last attempt should be reported.

### 11.2. Clinical Laboratory Tests

The clinical laboratory and other tests relating to safety to be performed during the study are described in the following table. The estimated total blood volume collected throughout the study (for clinical laboratory tests) is expected to be approximately 30 mL for safety serum chemistry and hematology laboratory evaluations.

**Table 5: Clinical Laboratory and Other Assessments**

Assessment	Study Visit	Description
Hematology	Baseline/Week 0 Week 52 (or ET)	Blood samples (5 mL) will be collected. Hematology parameters include: hemoglobin, hematocrit, mean corpuscular volume (MCV), mean corpuscular hemoglobin concentration (MCHC), red blood cell (RBC) count, white blood cell (WBC) count, WBC differential count, and platelet count.
Serum Chemistry	Baseline/Week 0 Week 52 (or ET)	Blood samples (10 mL) will be collected (fasting is not required). Routine serum chemistry parameters include alkaline phosphatase, albumin, blood urea nitrogen, calcium, carbon dioxide, chloride, creatinine, $\gamma$ -glutamyl transferase, glucose, inorganic phosphorus, potassium, alanine aminotransferase (ALT), lactate dehydrogenase, aspartate aminotransferase (AST), sodium, total bilirubin, and total protein.
Urinalysis	Baseline/Week 0 Week 52 (or ET)	Urinalysis will be performed using sponsor-supplied dipsticks, including leukocytes, specific gravity, pH, protein, ketones, glucose, nitrite, blood, urobilinogen, and bilirubin. If nitrite, blood, or protein tests are positive, a microscopic examination will be performed.
Serum pregnancy test (if applicable)	Baseline/Week 0 Week 52 (or ET) Safety Follow-Up	Serum pregnancy test will be performed for all female subjects of childbearing potential.
Urine pregnancy test (if applicable)	Week 4 Week 12 Week 24	Urine pregnancy test will be performed for all female subjects of childbearing potential.

Estimated glomerular filtration rate (eGFR) will be calculated by the central laboratory using Modification of Diet in Renal Disease (MDRD).

### 11.3. Columbia-Suicide Severity Rating Scale (C-SSRS)

The C-SSRS will be performed at every visit. Full details on how this assessment is to be performed will be provided in the study manual.

While the C-SSRS can provide valuable information as to the presence and intensity of suicidal ideation, determining the need for, and appropriate level of, therapeutic intervention depends on clinical judgment. The Joint Commission has published guidelines for treating suicidal ideation, “Sentinel Event Alert 56: Detecting and treating suicide ideation in all settings,” along with other resources that may prove useful to the investigator, available at: [https://www.jointcommission.org/sea\\_issue\\_56/](https://www.jointcommission.org/sea_issue_56/).

Subjects should also be monitored for depression, depressed mood, confusional state, and/or apathy, as well as suicidal ideation or behavior. New or worsening depression should be captured as an adverse event and treated appropriately per the Investigator's obligation and judgement.

## 12. EVALUATIONS BY VISIT

A schedule of study evaluations is provided in [Appendix A](#).

All study visits should occur on the day scheduled  $\pm$  2 days.

### 12.1. Baseline/Week 0

Potential subjects for the study will be fully informed about the nature of the study and possible AEs. Subjects who wish to participate in the study must read and understand the consent form and sign the document after the investigator has answered all questions to the candidate's satisfaction. Further procedures can begin only after the consent form has been signed.

The Week 16 Visit of Study ADS-AMT-MS301 will serve as the Baseline/Week 0 study visit of Study ADS-AMT-MS303 for those subjects who consent to participate. Per the Schedule of Events in [Appendix A](#), procedures that are shared between Study ADS-AMT-MS301 (Week 16 Visit) and the Baseline/Week 0 visit of the present study do not need to be repeated and the data will be captured in both studies.

The following procedures will be performed to establish each subject's qualifications for enrollment into the study:

- The subject is fully informed about the study and gives written informed consent to participate in the study
- Review inclusion/exclusion criteria and evaluate initial subject eligibility
- Record demographic information
- Medical history with an emphasis on the subject's MS and walking impairment, and past treatments for these conditions; alcohol and drug use, other neurological diseases, psychiatric disorders including Major Depressive Disorder or symptom (eg, hallucinations, agitation, paranoia, suicidal ideation), history of seizures, stroke or transient ischemic attack (TIA); history of myocardial infarction (MI) or congestive heart failure (CHF); and history of cancer
- Record all medications currently taken
- Assess and record AEs
- Complete physical examination
- Obtain subject weight in kilograms
- Vital signs (blood pressure, respiratory rate, heart rate, and temperature)
- Blood sample for central laboratory analysis including hematology, serum chemistry, and eGFR
- Urinalysis

- Blood sample for serum pregnancy test in female subjects of childbearing potential
- MSWS-12, T25FW, TUG, and 2MWT assessments (Full details on how individual efficacy assessments are to be performed will be provided in the study manual. These assessments are to be done in this order.)
- Administer the C-SSRS (administration instructions and forms will be provided in the study manual)
- Dispense study drug (1 wallet and 1 bottle)

## 12.2. Telephone Visit at Week 2

- Assess and record any changes in concomitant medications
- Assess and record AEs
- Remind subject to start taking capsules from the bottles
- If necessary, schedule an unscheduled visit

## 12.3. Visit at Week 4

- Assess and record concomitant medications
- Assess and record AEs
- Vital signs (blood pressure, respiratory rate, heart rate, and temperature)
- Urine sample for urine pregnancy test in females of childbearing potential
- C-SSRS
- Collect used/unused blister wallet and bottle and evaluate compliance
- Dispense study drug (2 bottles)

## 12.4. Visit at Week 12

- Assess and record concomitant medications
- Assess and record AEs
- Symptom-directed physical examination, as needed
- Vital signs (blood pressure, respiratory rate, heart rate, and temperature)
- Urine sample for urine pregnancy test in females of childbearing potential
- MSWS-12, T25FW, TUG, and 2MWT assessments (Full details on how individual efficacy assessments are to be performed will be provided in the study manual. These assessments are to be done in this order.)
- C-SSRS
- Collect used/unused bottles and evaluate compliance
- Dispense study drug (3 bottles)

## 12.5. Visit at Week 24

- Assess and record concomitant medications
- Assess and record AEs
- Symptom-directed physical examination, as needed
- Vital signs (blood pressure, respiratory rate, heart rate, and temperature)
- Urine sample for urine pregnancy test in females of childbearing potential
- MSWS-12, T25FW, TUG, and 2MWT assessments (Full details on how individual efficacy assessments are to be performed will be provided in the study manual. These assessments are to be done in this order.)
- C-SSRS
- Collect used/unused bottles and evaluate compliance
- Dispense study drug (7 bottles)

## 12.6. Telephone Visit at Week 38

- Assess and record any changes in concomitant medications
- Assess and record AEs

## 12.7. Visit at Week 52

- Assess and record concomitant medications
- Assess and record AEs
- Complete physical examination
- Obtain subject weight in kilograms
- Vital signs (blood pressure, respiratory rate, heart rate, and temperature)
- Blood sample for central laboratory analysis including hematology, serum chemistry, and eGFR
- Urinalysis
- Blood sample for serum pregnancy test in female subjects of childbearing potential
- Administer the EDSS (administration instructions and forms will be provided separately)
- MSWS-12, T25FW, TUG, and 2MWT assessments (Full details on how individual efficacy assessments are to be performed will be provided in the study manual. These assessments are to be done in this order.)
- C-SSRS
- Collect bottles and evaluate compliance

